7.2 Adherence and protocol deviations

Adherence to intervention will be monitored at Visit 2 and 3 and via online questionnaires. Adherence will be presented as part of the results.

Deviations from the protocol including violations of inclusion/exclusion criteria will be assessed as “minor” or “major.” Major protocol deviations are defined as those deviations from the protocol likely to have an impact on the perceived efficacy and/or safety of study treatments, and therefore, would result in a patient being excluded from the per protocol population. Major deviations will be identified and finalized prior to database lock and documented. Examples of major protocol deviations and any action to be taken regarding the exclusion of patients or affected data from specific analyses are outlined below. Complete details will be included in a separate Protocol Deviation Plan, which will be appended to the final version of this SAP.

7.3 Major Protocol Deviation Population Exclusions

Randomized but did not take any study medication: Exclude from statistical analyses and per protocol analyses

Consumed the incorrect study medication per randomization scheme: Exclude from per protocol analyses

Major Protocol Violations: Exclude from per protocol analyses

Non-compliant (< 80% compliant with intended study medication): Exclude from per protocol analyses

Took prohibited medication that impacts efficacy: Exclude from per protocol analyses.

7.4 Analysis populations

The primary analyses will be performed on all subjects randomized in the trial (intention to treat). Sensitivity analyses will be performed on the per protocol population.

8. Trial Population

8.1 Screening data

Possible subjects are pregnant women suffering with HG.

We will collect data on all patients who were assessed for eligibility as to describe the representativeness of the trial population. If patients do not wish to be enrolled in the trial, the reason will be registered.

8.2 Eligibility

Inclusion criteria:

- Written informed consent obtained before any trial related procedures are performed
- Female age >18 years
- Pregnant woman with gestational age between 5+0 and 11+6
- Nausea and vomiting without other obvious reason
- PUQE-24 score ≥ 13 OR

CONFIDENTIAL

PUQE-24 score ≥ 7 AND

1. weight loss $>5\%$ OR
2. hospitalization due to nausea and vomiting of pregnancy

Compliance with this criterion on any given day within 3 days prior to screening (possibly not compliant with this criterion on day of randomization)

- Singleton pregnancy
- The subject must be willing and able to comply with trial protocol

Exclusion criteria:

- Mola pregnancy, multiple gestation or non-vital pregnancy
- Nausea and vomiting of other aetiology than NVP
- Allergic to selective 5-HT₃-receptor antagonists
- Ongoing treatment with antidepressant medication
- Pre-existing diagnosis of chronic kidney disease, diabetes type 1 or 2, significant cardiac disease (incl. long QT syndrome), epilepsy, HIV. In case of other pre-existing conditions subjects might be excluded based on individual assessment by an MD
- Elevated liver enzymes (ALAT/ASAT >150)
- Elevated creatinine (>100)
- ECG showing long QT-syndrome (QTc >460 msek)
- Alcoholism; subject drinks more than recommended by health authorities
- Not able to take medicine orally
- Not able to understand spoken and written Danish
- Participation in another investigational drug trial within current pregnancy

8.3 Recruitment

We will report number of subjects assessed for eligibility, number and reasons for exclusion, and number of subjects randomised to each group.

8.4 Withdrawal/follow-up

Number, time and reason for discontinuation (withdrawal from intervention), lost-to-follow-up and final number analysed will be reported. Discontinued subjects and lost-to-follow-up will not be replaced.

8.5 Baseline patient characteristics

Baseline characteristics to be summarized in Table 1:

- History of HG in previous pregnancy
- Maternal age

CONFIDENTIAL

- Weight, kg
- BMI, kg/m²
- Gestational age at randomisation, w+d
- PUQE-24 score at randomisation
- NVPQOL at randomisation
- HELP score at randomisation
- EQ-5D at randomisation
- 7 days PSQI at randomisation

9. Analysis

9.1 Outcome definitions

Primary endpoint:

The coprimary endpoints are:

- Change in PUQE-24 score from baseline to Day 2 (short term)
- Change in PUQE-24 score from baseline to Day 14(+/-1) (long term) in the mirtazapine group versus the placebo group.

The change in PUQE-24 score is calculated as baseline score minus Day 2 score and baseline score minus Day 14(+/-1) score, respectively. Baseline values will be recorded at randomisation.

The null hypothesis will be rejected if we find a difference of 2 or more on either short or long term or both.

PUQE-24 score (Pregnancy-Unique Quantification of Emesis and Nausea) is a validated scoring system used to grade the severity of NVP. PUQE-24 score consists of three elements:

- 1) number of hours with nausea within the last 24 hours (from none at all to more than 6 hours),
- 2) number of vomiting episodes in the last 24 hours (from 0 to >6 times), and
- 3) number of retching episodes without vomiting within the last 24 hours (from 0 to >6 times).

Each element gives a sub-score from 1 to 5 points and the total score is calculated by adding the three sub-scores giving a total score ranging from 3 to 15.

The condition is graded as mild if the score is 3-6, moderate with a score of 7-12 and severe if the score is 13-15(3). See Appendix 1.

Secondary endpoints:

- Change in PUQE-24 score from baseline to Day 2 in the ondansetron group versus the placebo group.
- Change in PUQE-24 score from baseline to Day 14(+/-1) in the ondansetron group versus the placebo group.
- Change in PUQE-24 score from baseline to Day 2 in the mirtazapine group versus the ondansetron group.
- Change in PUQE-24 score from baseline to Day 14(+/-1) in the mirtazapine group versus the ondansetron group.
- Area under the curve for PUQE-24 score during the intervention in the three different groups.
- Change in PUQE well-being score during the intervention in the three different groups.
- Change in daily nausea VAS during the intervention in the three different groups.
- Change in number of daily vomiting episodes during the intervention in the three different groups.
- Change in NVPQOL (health-related quality of life for nausea and vomiting during pregnancy) from baseline to Day 7(+/-1) and baseline to Day 14(+/-1) in the three different groups.
- Change in HELP score (hyperemesis level prediction) from baseline to Day 7(+/-1) and baseline to Day 14(+/-1) in the three different groups.
- Change in EQ-5D (health-related quality of life) from baseline to Day 7(+/-1) and baseline to Day 14(+/-1) in the three different groups.
- Change in past 7 days PSQI (Pittsburg Sleep Quality Index) from baseline to Day 7(+/-1) and baseline to Day 14(+/-1) in the three different groups.
- Patient satisfaction with treatment VAS on Day 7(+/-1) and Day 14(+/-1) in the three different groups.

CONFIDENTIAL

- Change in patient consideration of termination of pregnancy from baseline to Day 7(+/-1) and baseline to Day 14(+/-1) in the three different groups.
- Frequency of and time to treatment failure in the three different groups.
- Frequency of request for dosage increase in the three different groups.
- Average daily use of rescue medication during the intervention in the three different groups.
- Number of days of sick leave during the intervention in the three different groups.
- Number of treatments with i.v.-fluids during the intervention in the three different groups.
- Number of days of hospitalizations during the intervention in the three different groups.
- Weight change in kg from baseline to Day 7(+/-1) and baseline to Day 14(+/-1) in the three different groups.
- Frequency of request for continuation of trial medication after end of intervention in the three different groups.
- Birth outcome (birth weight, gestational age, APGAR, umbilical cord pH, placenta weight, sex, hospitalizations on neonatal ward during the first month post-partum). This endpoint will not be double blind on all patients since patients can be unblinded after end of the intervention. The statistician will remain blinded.

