6.4 Sample size

The trial is dimensioned to find a difference of 2 in PUQE-24 score change from baseline to Day 2 (short term) and/or from baseline to Day 14(+/-1)(long term) between the mirtazapine group and the placebo group with 80% power based on a standard deviation (SD) of change of PUQE-24 score of 3, a type 1 error rate of 2,5% and 25% drop-out. The reason for the 2,5% type 1 error rate is that we want to test 2 hypotheses; effect of mirtazapine versus placebo short and long term on HG.

Thus, we will have to include 57 subjects in each of the 3 groups, which we round up to 60 subjects, equivalent of 180 subjects all together.

A SD of 3 is a conservative estimate based on the placebo-controlled trial with doxylamine-pyridoxine(1,2).

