6.5 Framework

Two-sided equality test with the null hypothesis is that the expected difference of the effects of mirtazapine and placebo is zero.

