7.1 Confidence intervals and P values

We aim for a p-value of 0.025 for each of the two primary outcomes. This will give a total type 1 error rate of 5% for the hypothesis.

Results will be reported with 95% confidence intervals.

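### The primary endpoints carry two incompatible rejection rules; the one that requires an observed PUQE-24 difference of 2 has 50% power per endpoint at the design effect, not 80%

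*SAP*

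**What the plan says.** SAP 9.1 defines the two coprimary endpoints (change in PUQE-24 from baseline to Day 2 and to Day 14, mirtazapine versus placebo) and then gives a decision rule: "The null hypothesis will be rejected if we find a difference of 2 or more on either short or long term or both". Protocol 5.3 has the same sentence. It mentions no p-value, standard error or confidence interval.

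Other sections describe a significance test:

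- SAP 6.5: "Two-sided equality test with the null hypothesis is that the expected difference of the effects of mirtazapine and placebo is zero".
- SAP 7.1: "We aim for a p-value of 0.025 for each of the two primary outcomes", followed by "This will give a total type 1 error rate of 5% for the hypothesis".
- SAP 9.2 and Protocol 13 estimate the group differences from a linear mixed model and base the comparisons on its standard errors.

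The figure of 2 also appears in the sample-size sections (SAP 6.4, Protocol 8.3): "The trial is dimensioned to find a difference of 2 in PUQE-24 score change from baseline to Day 2 (short term) and/or" to Day 14, with "80% power based on a standard deviation (SD) of change of PUQE-24 score of 3" and "a type 1 error rate of 2,5% and 25% drop-out". The result is that "we will have to include 57 subjects in each of the 3 groups, which we round up to 60 subjects".

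Neither document says that 2 is only a benchmark for clinical relevance, that both conditions must hold, or which rule takes precedence.

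**The concern.** The plan gives two success criteria for the same endpoints, and they can disagree. One compares the point estimate with 2; the other compares the estimate with its standard error. In a trial sized for 80% power, the smallest significant estimate is well below the difference used for planning. Making the planning difference the hurdle therefore discards much of the power the sample size was meant to buy.

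Two consequences follow. First, a real effect of the planned size would be missed half the time on each endpoint. Second, an estimate between the test's critical value and 2 rejects the null under SAP 6.5 and 7.1 but not under SAP 9.1 and Protocol 5.3. The main conclusion would then depend on which section was chosen once results were known. The rule also ignores precision, so it does not hold the type 1 error at any set level.

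**Working it through.** **Inputs.** True difference 2, SD of change 3, power 80%, type 1 error 2.5% per endpoint and 25% drop-out (SAP 6.4, Protocol 8.3); two-sided test (SAP 6.5); 60 per arm. The evaluable number is 60 × 0.75 = 45 per arm. Normal approximation, with z(0.9875) = 2.2414 and z(0.80) = 0.8416.

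**1. Reproduce the stated sample size.**
n = 2 × (2.2414 + 0.8416)² × 3² / 2² = 42.77 per arm. Dividing by 0.75 gives 57.03, which matches the stated 57. (Rounding up to 43 first gives 58.) A one-sided 2.5% test needs 36 per arm, or 48 after drop-out, which does not match. The trial was therefore sized, per endpoint, for the two-sided 2.5% test and not for a rule on the observed difference.

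**2. Where the test rejects.**
SE = 3 × √(2/45) = 0.632. Critical observed difference = 2.2414 × 0.632 = 1.42. If all 60 per arm are evaluable, SE = 0.548 and the critical difference is 1.23.

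**3. Power per endpoint at a true difference of 2.**
- Written rule: P(estimate ≥ 2 | true 2) = 0.50. This holds for any n and SD, because a symmetric unbiased estimate falls below its true value half the time.
- Test: Φ(2/0.632 − 2.2414) = Φ(0.921) = 0.82 (0.81 with the t distribution).
- A simulation of 1,000,000 estimates gave 50.0% and 82.2%.
- The written rule reaches 80% per endpoint only at a true difference of 2 + 0.8416 × 0.632 = 2.53.

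**4. Power for at least one endpoint, both true differences 2.** The documents give no correlation between the two estimates, so a range is assumed (45 per arm).

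| Correlation | Written rule | Two-sided test at 0.025 |
|---|---|---|
| 0 | 75% | 97% |
| 0.3 | 70% | 95% |
| 0.5 | 67% | 93% |
| 0.7 | 63% | 90% |
| 0.9 | 57% | 87% |

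**5. How often the rules disagree.** At a true difference of 2, the probability that an endpoint's estimate lies between the critical value and 2 is 0.821 − 0.500 = 0.32 with 45 per arm, and 0.921 − 0.500 = 0.42 with 60 per arm.

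**6. Type 1 error of the written rule.** With 45 per arm and SD 3, P(estimate ≥ 2 | true 0) = 1 − Φ(3.16) = 0.08%, or 0.16% if differences in either direction count. The level moves with the SD: the two-sided figure passes 2.5% once the SD exceeds 2 / (2.2414 × √(2/45)) = 4.23, and is 5.8% at an assumed SD of 5.

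**The case against.** The best defence is that the sentence is a drafting slip. The sample-size sections speak of finding a difference of 2 in the sense of detecting it by a test, and SAP 9.1 may repeat that idiom loosely. A rule on the point estimate alone would leave SAP 6.5, SAP 7.1 and the standard errors in SAP 9.2 with no role in the decision. On that reading the sizing is sound and the 50% never materialises. This is plausible, and the sizing is indeed sound. But the sentence says in both documents when the null hypothesis is rejected, and it is the most explicit rejection statement in either. SAP 7.1 only says what p-value is aimed for.

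Reading the two rules as joint conditions does not help. Under the design assumptions the significance cut-off of 1.42 lies below 2, so power per endpoint stays at 50%.

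The wording also allows success on either endpoint, so the trial-level loss is smaller than the per-endpoint figure suggests. That is correct, but the rule still reaches at most 75% at non-negative correlations.

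False rejection under the written rule is fairly remote. At SD 3 an observed difference of 2 stays significant until fewer than about 23 per arm remain (2 × (3 × 2.2414 / 2)² = 22.6), roughly a 62% loss from 60. The SD would have to exceed 4.2, while the plan calls 3 conservative. The practical harm is lost power and an undetermined conclusion, more than a raised type 1 error.

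**Conclusion.** The concern holds and must be fixed. The plan states a rejection rule for its primary endpoints that conflicts with its own two-sided 2.5% test and with the basis on which the trial was sized. Applied literally, the rule cuts power per endpoint at the design effect from 82% to 50%, and power for at least one endpoint from 90-97% to 63-75% (from 87% to 57% at a correlation of 0.9). For a given endpoint, the two rules would disagree in about 32% of trials with 45 evaluable per arm, rising to 42% with 60.

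The 50% needs only a symmetric, unbiased estimate. The other figures assume SD 3, the same number evaluable on Day 2 and Day 14, a two-sample standard error in place of the mixed-model one, and assumed correlations between the endpoints. A more precise mixed-model estimate would lower the critical difference and widen the zone of disagreement. The sample size itself is not at fault.

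**What to change.** Delete the sentence in SAP 9.1 and Protocol 5.3 and put the same replacement in both, for example:

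> For each coprimary endpoint, the null hypothesis of no difference between mirtazapine and placebo is rejected if the two-sided p-value from the linear mixed model is below 0.025.

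Stating 0.025 in the sentence lets the protocol stand without pointing to the SAP. Keep 2 points as the planning difference and, if the authors confirm that this was the intention, as a benchmark for discussing clinical relevance. If they do want an observed difference of 2 as an added condition for success, they should say so and report the resulting power, which is 50% per endpoint at a true difference of 2.

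The correction should be made before treatment codes are joined to the data. It costs one sentence in each document and needs no extra data or patients.

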9.2 Analysis methods

The primary analysis will consist of a linear mixed effects model taking the full longitudinal design into account. The model will be adjusted for site (categorical variable) due to the stratified design. Subjects will be included in the analysis irrespectively of their adherence to the protocol. The treatment effect for the primary outcome will be presented as the average difference between the mirtazapine and placebo groups in PUQE-24 score change from baseline to day 2 and from baseline to day 14. These comparisons will be based on the standard errors from the linear mixed model. Sensitivity analyses will be performed using multiple imputation where the imputation model will include all available baseline variables.

The statistician performing the analyses will remain blinded until the analyses results are closed.

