6.2 Discussion of Design

The existing clinical studies on treatment for NVP generally have two arms; an IMP is tested against placebo or an active comparator. In designing this study with three arms, we can compare both mirtazapine and ondansetron to placebo and thus spare a placebo group. Furthermore, we can gain data on mirtazapine compared to an active comparator (ondansetron).

The intervention will last 14 days which is also seen in other clinical trials on treatment of NVP(39). This is estimated to be sufficient time to observe the effect of the intervention. An effect is expected within days after initiating treatment, thus at the visit on Day 7 a potential effect will have reached a stable level. If the treatment is not sufficiently effective it will be possible to increase the dosage of the IMPs.

In the national guideline on HG ondansetron 8 mg is to be administered twice daily with optional increase to a maximum total dosage of 32 mg per day. By allowing an increase in administration to exactly that our intervention will reflect current practice.

In most of the case reports on mirtazapine as treatment for HG, dosages of up to 15 mg daily have been effective. However, in a few cases the patients were started on mirtazapine 30 mg daily. Thus, to not disregard a possible effect due to inadequate dosage, we consider it relevant to make dosage increase to 30 mg daily optional.

The option of dosage increase might also ensure that the subjects stay in the trial even if they do not experience the desired symptom relief during the first week. However, there is still a concern that due to drop-outs and missing data the dataset may be incomplete at the end of the trial. As a consequence, we risk that a potential clinically significant effect of an IMP might not be shown as statistically significant. To minimize this risk, we will have two primary endpoints: a change in PUQE-score from baseline to Day 2 and from baseline to Day 14(+/-1). In this manner, we will be able to show a potential effect on Day 2, even if we do not have sufficient data to show it at the end of the intervention (Day 14). Furthermore, we have added 'treatment failure' as a secondary outcome, and subjects will be prompted to indicate if insufficient symptom relief was the reason for drop-out.

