12.2 Laboratory Data

Values from blood and urine samples and ECG will obtained from the medical journal and be entered manually into the e-CRF.

CONFIDENTIAL

13. Statistical evaluation

The primary analysis will consist of a linear mixed effects model taking the full longitudinal design into account. The model will be adjusted for site (categorical variable) due to the stratified design. Subjects will be included in the analysis irrespectively of their adherence to the protocol. The treatment effect for the primary outcome will be presented as the average difference between the mirtazapine and placebo groups in changes in PUQE-24 score from baseline to Day 2 and from baseline to Day 14. These comparisons will be based on the standard errors from the linear mixed model. Sensitivity analyses will be performed using multiple imputation where the imputation model will include all available baseline variables.

Before the randomisation code will be added to the cleaned dataset, a prespecified statistical analysis plan (SAP) will be elaborated and accepted by the statistician and investigators.

All data will be described including data-incompleteness as well as reasons for data-incompleteness. Data will be analysed blinded by the statistician. Any changes to the statistical analysis plan will be described in any future publications.

For further information on the final analysis refer to the SAP.

14. End of trial

Within 90 days after the trial completion the sponsor must inform the Danish Health Authorities and Ethics Committee about the completion. The result of the trial must be submitted within 12 months.

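### SAP 9.2 leaves the Day 0 PUQE-24 means free or common across arms; constraining them equal is an optional precision gain of about 0–35% in variance, at no cost in data

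*SAP*

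**What the plan says.** SAP 9.2 describes the primary analysis as a linear mixed effects model that takes the full longitudinal design into account. The only adjustment it names is site: "The model will be adjusted for site (categorical variable) due to the stratified design". The effect is to be reported as the difference between mirtazapine and placebo in change from baseline to Day 2 and to Day 14, using the model's standard errors. Protocol section 13 describes the same model and defers to the SAP: "For further information on the final analysis refer to the SAP".

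The randomisation-day score appears in two other places. SAP 9.1 uses it to define the outcome: "The change in PUQE-24 score is calculated as baseline score minus Day 2 score and baseline score minus Day 14(+/-1) score, respectively". As a baseline variable it also enters the imputation model of the sensitivity analysis in SAP 9.2. Neither document says whether the Day 0 arm means in the primary model are free or common.

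The sample size in SAP 6.4 rests on the raw change score, "based on a standard deviation (SD) of change of PUQE-24 score of 3, a type 1 error rate of 2,5% and 25% drop-out", with no allowance for baseline adjustment.

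**The concern.** On the natural reading of SAP 9.2, Day 0 is one of the responses in the mixed model. That alone does not use the baseline score to improve precision. If each arm has its own Day 0 mean and the data are complete, the contrast is simply the difference in mean raw change, and a chance imbalance at Day 0 passes into it in full. If the three arms share one Day 0 mean, the follow-up difference is corrected for that imbalance through the regression of follow-up on baseline.

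Both models satisfy the present wording. In a given dataset they can give different estimates, standard errors and p-values for both co-primary contrasts. What is at stake is precision, and the pre-specification of a choice that Protocol 13 says the SAP should settle before the randomisation code is added to the data.

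**Working it through.** **Inputs from the documents.** Difference 2 and SD of change 3 (SAP 6.4); two-sided test (SAP 6.5); 0.025 for each co-primary endpoint (SAP 7.1); 25% dropout and 60 randomised per arm (SAP 6.4), hence 60 × 0.75 = 45 evaluable.

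**Assumed, because the documents do not give them.** The correlation r between the Day 0 and follow-up scores, and the ratio k = follow-up SD / baseline SD.

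**1. The plan's own figure.** n = 2 × [3 × (2.241 + 0.842)/2]² = 42.77 evaluable per arm; 42.77/0.75 = 57.03. The stated 57 reproduces.

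**2. Free Day 0 means, complete data.** SE = 3 × √(2/45) = 0.632. Two-sample t-test power is 80.9%. The half-width of the 95% interval is 1.987 × 0.632 = 1.26 points.

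**3. Common Day 0 mean.** Set the baseline SD to 1.
- Variance of raw change: 1 + k² − 2rk
- Variance with a common Day 0 mean: k²(1 − r²)
- Share of variance saved: (1 − rk)² / (1 + k² − 2rk)

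With known covariance the share cannot be negative, and it is zero when rk = 1. Example: r = 0.5, k = 1 gives 0.25/1 = 25%, so SE = 0.632 × √0.75 = 0.548.

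| k | r | Variance saved | SE | Power |
|---|---|---|---|---|
| 1 | 0.3 | 35% | 0.510 | 94.8% |
| 1 | 0.5 | 25% | 0.548 | 91.3% |
| 1 | 0.7 | 15% | 0.583 | 87.3% |
| 1.25 | 0.3 | 22% | 0.560 | 89.9% |
| 1.25 | 0.5 | 11% | 0.598 | 85.5% |
| 1.25 | 0.7 | 2% | 0.626 | 81.7% |
| 1.5 | 0.3 | 13% | 0.590 | 86.4% |
| 1.5 | 0.5 | 4% | 0.621 | 82.5% |
| 1.5 | 0.7 | 0.2% | 0.632 | 81.0% |

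The 95% half-width therefore lies between 1.01 and 1.26 points.

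**4. Which cells are plausible.** With SD of change 3, the implied baseline SD is 3/√(1 + k² − 2rk). For r = 0.5 this gives baseline/follow-up SDs of 3.00/3.00 (k = 1), 2.62/3.27 (k = 1.25) and 2.27/3.40 (k = 1.5). A uniform spread over 7–15 has SD 2.58, and over 3–15 it has SD 3.74. The entry threshold of 7 points towards k above 1, where the gain is smaller. It does not fix k, because SAP 8.2 lets the severity criterion lapse by Day 0: "Compliance with this criterion on any given day within 3 days prior to screening (possibly not compliant with this criterion on day of randomization". Nor can high correlations be ruled out: r = 0.6 with k = 1.5 needs SDs of only 2.49/3.74, yet saves just 0.7%.

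**5. Day 14 with dropout.** I used an information-matrix calculation for Days 0–14, with 60 per arm, 25% dropout spread over Days 3–14, and an assumed correlation between follow-up days of 0.5 + 0.5 × 0.7^lag. For r = 0.3/0.5/0.7 the Day 14 variance falls by 31/21/12% (k = 1), 19/9/1.5% (k = 1.25) and 11/3/0.2% (k = 1.5). The Day 2 reductions equal those in the table.

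**The case against.** The strongest reply is that this is a preference between two valid forms of one model. Neither form is biased, the difference in mean change is the target in both, and the planned power is met without the constraint. The text already supplies most of the handling: a longitudinal mixed model, change from baseline, and missing data addressed by that model (SAP 9.3). All of that stands, so the point is optional.

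It also stands that the gain may be negligible. SAP 6.4 calls an SD of 3 conservative, and with a smaller SD the unadjusted power is already higher.

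The constraint alone also does not guarantee good error control. In a check with an unstructured covariance estimated by maximum likelihood, a Wald z test and 25% dropout (1,500 simulated trials per setting), Day 14 type I error was 4.1%, 3.3% and 2.9% in three settings, against a nominal 2.5% (Monte Carlo SE about 0.4). The free-mean model probably shares this small-sample problem. It is a reason to state the estimation method too.

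Three stronger readings are tempting, and the documents do not support them.
- A reader might infer that the trial is underpowered or the analysis wrong without baseline adjustment. The 80.9% in step 2 shows otherwise.
- A reader might take the constraint as an answer to the Protocol 6.2 worry about Day 14, where the Day 2 endpoint is added because "we will be able to show a potential effect on Day 2, even if we do not have sufficient data" at the end of the intervention. That passage concerns missing scores, and a common Day 0 mean recovers none of them.
- A reader might credit the constraint with keeping more subjects, in line with SAP 7.4 ("The primary analyses will be performed on all subjects randomized in the trial (intention to treat"). The free-mean model keeps subjects with only a Day 0 score as well.

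What the reply does not remove is that the constrained model is at least as precise with known covariance, is justified by randomisation, and uses a score already collected.

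**Conclusion.** The concern holds as an optional improvement. SAP 9.2 leaves open whether the Day 0 means are free or common. The free version is valid and meets the stated power, but it can leave precision unused in both co-primary contrasts.

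The size of the loss is unknown. It is about 0–35% of the variance over assumed r = 0.3–0.7 and k = 1–1.5, and near zero when rk is close to 1. The figures assume an SD of change of exactly 3 and 45 evaluable per arm, and the Day 14 reductions further assume the dropout and correlation pattern in step 5. The upper part of the range, including the 25% at r = 0.5 with equal SDs, should not be read as the expected gain.

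**What to change.** In SAP 9.2, specify a linear mixed model for daily PUQE-24 with categorical day, arm-by-day terms and site. Include Day 0 as a response with its mean constrained equal across the three arms, and take the Day 2 and Day 14 contrasts from this model. State that it is fitted by REML, name the covariance structure, and name a small-sample degrees-of-freedom method (for example Kenward-Roger or Satterthwaite).

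The cost is SAP wording only. The score is already recorded at Visit 1, no further data or subjects are needed, the estimand is unchanged, and the model has two fewer mean parameters (three Day 0 means become one).
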